1.1.2. SECONDARY OBJECTIVES

- To assess if the incidence rate of severe hypotensive (vasovagal/hypovolemia) adverse events according to the plasma center adverse event reporting system, based on the IQPP definitions, per donation in donors undergoing plasmapheresis in the experimental group is NOT inferior to that seen in donors in the control group
- To assess the incidence rate of significant hypotensive (vasovagal/hypovolemia) adverse events according to the plasma center adverse event reporting system, based on the IQPP definitions, relative to the actual plasma volume of plasma collected, comparing procedures in the experimental group and control group
- To study the time from the start of plasmapheresis "Begin Draw" to the first significant hypotensive (vasovagal/hypovolemia) adverse events according to the plasma center adverse event reporting system, based on the IQPP definitions, in the experimental group and the control group
- To assess the incidence rate of significant hypotensive (vasovagal/hypovolemia) adverse events according to the plasma center adverse event reporting system, based on the IQPP definitions, of procedures in the experimental group and in the control group in the subgroups of donors with a bodyweight of less than or equal to 130 lbs and those greater than 130 lbs
- To assess the incidence rate of significant hypotensive (vasovagal/hypovolemia) adverse events according to the plasma center adverse event reporting system, based on the IQPP definitions, of procedures in the experimental group and in the control group in the

Statistical Analysis Plan Version: 1.0 Date: 26-Apr-2020

subgroups of donors with a body mass index (BMI) of less than or equal to 30 and of those greater than 30

- To assess the incidence rate of significant hypotensive (vasovagal/hypovolemia) adverse events according to the plasma center adverse event reporting system, based on the IQPP definitions, of procedures in the experimental group and in the control group in the subgroups of donors defined by their respective status as a first-time donor or repeat donor
- To assess the incidence rate of significant hypotensive (vasovagal/hypovolemia) adverse events according to the plasma center adverse event reporting system, based on the IQPP definitions, of procedures in the experimental group and in the control group in the subgroups of donors defined by their gender
- To evaluate the total plasma volume collected per procedure in the experimental group and in the control group.

1.2. SUMMARY OF THE STUDY DESIGN

1.2.1. BACKGROUND

Prior to 1992, there was no standard nomogram used by all plasmapheresis devices. Each manufacturer produced their own unique nomogram. These various nomograms were based on the variables of height, weight, and hematocrit. Traditionally, the plasma collection operator used a series of lookup tables to determine the appropriate plasma collection volume and would enter this volume manually into the corresponding plasmapheresis device. These earlier nomograms had a number of benefits. The use of both height and weight to determine the target collection volume was a step toward incorporating BMI, ensuring that those who appeared to have less total Protocol No: TP-CLN-100467(AB)

Statistical Analysis Plan Version: 1.0 Date: 26-Apr-2020

plasma volume would donate less. These types of nomograms also utilized the donor's hematocrit to further tailor the collection volume to the donor's biometric data.

In addition to the lack of consistency between devices, the shortcoming of this approach was the stepwise calculation output. Prior to 1992, devices could not be programmed to automate all of the targeting steps. This left room for human error in the manual calculation of target collection volume. To reduce this error by simplifying the process, the nomogram variables (height, weight, and hematocrit) were grouped by ranges. However, this simplification led to a significant decrease in specificity. For example, a small change in weight, height, or hematocrit could change the range group the donor belonged to, thus, having a large impact on the target collection volume.

Despite this effort to reduce errors by simplifying the manual calculation, additional risk of miscalculation/human error has remained. Given the possibility of the same site using devices from different manufacturers, multiple versions of lookup tables on the donor floor could occur simultaneously. The risk of a nomogram being used with the wrong device prompted the Center for Biologics Evaluation and Research (CBER) to publish the current Food and Drug Administration (FDA) nomogram in 1992.

1.2.2. GENERAL STUDY DESIGN AND PLAN

This is a multicenter, randomized, prospective IDE clinical trial to evaluate the safety and effectiveness of a PPN feature using the NexSys® PCS during plasmapheresis. In an effort to prevent bias, the clinical trial will be blinded to select members of the sponsor study team in

ClinStatDevice

Statistical Analysis Plan Version: 1.0 Date: 26-Apr-2020

accordance with the blinding plan, and subjects will not be made actively aware to which group they have been randomized – however, subjects may be able to determine to which group they have been assigned and there is no practical way to hide this from them with certainty (e.g., collection volume in bottle, time of procedure). The clinical trial is designed to collect approximately 24,000 plasmapheresis procedures from around 5,000 - 6,000 donors. Donors will be randomized 1:1 to the experimental group undergoing plasmapheresis using NexSys® PCS with the PPN feature or the control group undergoing plasmapheresis using NexSys PCS® with YES® technology. As repeat donations by the same donor are expected, the donor will remain in the same study group during the entire course of the clinical trial. The sample size of the clinical trial may be reevaluated based on the number of donations and observed significant hypotensive (vasovagal/hypovolemia) adverse events according to the plasma center adverse event reporting system, based on the IQPP definitions. Prior to enrollment, all subjects will be required to provide written consent.

1.2.3. RANDOMIZATION

Donors will be randomized 1:1 to the experimental or control groups. As repeat donations by the same donor are expected, the donor will remain in the same study group during the entire course of the clinical trial.

The randomization will target equal allocation of the number of donors in each study group per site. Adverse Event (AE) incidence rates and the expected proportions in the sample groups are expected to be drastically different between the following groups: Males vs females and first-time

Statistical Analysis Plan Version: 1.0 Date: 26-Apr-2020

donors vs repeat donors. Thus, randomization will be further stratified by the donor's gender and first-time donor status. As the expected number of repeat donations is expected to be highly correlated with the AE incidence, stratification by expected number of repeat donations for the repeat donor groups might be done as well. This final step of the stratification will be possible under the condition of the availability of historic data through which calculation of expected number of donations for repeat donors could be completed.

Stratified permuted block randomization procedure with variable block sizes will be used. The sizes of the blocks will randomly vary with possible values of 6, 8 or 10.

Allocation of subjects to clinical trial groups will proceed based on the block randomization procedure as outlined above. Once subjects are enrolled, they will be randomly assigned to the experimental or control group and the assignment information will be synchronized with the NexLynk® system. The randomization system will provide a confirmation report containing the subject number and the randomization code. Sponsor will be monitoring the implementation of the randomization procedure for the QC purposes.

Allocation Miss-Assignment means administration of a study procedure other than that which was provided by the randomization assignment. Example: a subject was randomized to the Control group but received the Experimental procedure.

In the event of a protocol deviation caused by Allocation Miss-Assignment the following procedure will be used:

• If the Allocation Miss-Assignment happens at the first donation, the donor will be allowed to continue donating to the study group associated with the administered

ClinStatDevice

Statistical Analysis Plan Version: 1.0 Date: 26-Apr-2020

procedure. Their study group assignment will be changed to the administered procedure group and the donor will be expected to donate only in this study group.

• If the donor happens to donate in both study groups (Allocation Miss-Assignment happens after the first donation or it happens twice) the donor will be discontinued. The study group associated with the donor will follow the procedure that the donor administered at the first donation.

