2.2. DEFINITIONS OF ANALYSIS DATA SETS

2.2.1. DEFINITIONS

Study Donor is defined as a study participant who consented to the study and was randomized to a study procedure (control or experimental).

Statistical Analysis Plan Version: 1.0 Date: 26-Apr-2020

Study Donation is defined as a donation that took place during the course of the study and is associated with the study donor.

Non-Study Donation is defined as a donation that took place either before the study start date or after the last date of the study.

Study Adverse Event is defined as an adverse event that was reported to be associated with the study donation.

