2.2.2. STUDY POPULATIONS

The ITT data set will consist of all study donations were the apheresis procedure was started by "Begin Draw" on the NexSys® PCS device. The ITT population will include all Study Adverse Events.

The Modified Intent to Treat (MITT) data set is a subset of the ITT data set which consists of all complete study donations, as well as all donations associated with a moderate or severe adverse event [not just hypotensive (vasovagal/hypovolemia)] defined according to the IQPP and associated with the study donations. A donation is considered complete if the total plasma volume collected is at least 200 mL. A donation is considered incomplete if the total plasma volume collected is less than 200 mL.

The Per-Protocol (PP) data set will consist of all donations without major protocol deviations where the apheresis procedure is successfully completed collecting at least 90% of the target plasma volume, as well as all study donations associated with a moderate or severe adverse event [not just hypotensive (vasovagal/hypovolemia)] defined according to the IQPP.

Statistical Analysis Plan Version: 1.0 Date: 26-Apr-2020

The Extended AE Population (EAEP) is defined as consisting of ITT population with the addition of all the AEs that were reported as associated with Non-Study donations in donors previously enrolled in the study and reported within two calendar weeks post study last day.

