3.1.1. STATISTICAL ANALYSIS METHOD

Given the nature of the data where donors contribute multiple data samples (donations), Generalized Estimation Equations Logistic Regression (GEE Logistic) framework for the repeat measures will be used (Halekoh, 2006; Yan J, 2004). The regression equation is presented below with Patient ID representing the random effect, and plasmapheresis method (study group) being fixed effect. Additional covariates are age, gender, BMI, and first-time donor status.

 $Logit(P(AE_{i,t}=1)) = \beta_0 + \beta_{Treatment} \times Treatment_i + \beta_{Age} \times Age_{i,t} + \beta_{Gender} \times Gender_i + \beta_{First \ Comer} \times First \ comer_{i,t} + \beta_{BMI} \times BMI_{i,t} + \varepsilon_{i,t},$

Corr(AE_{i,j}, AE_{i,k}) is exchangeable across all donors.

$$Corr(AE) = \begin{bmatrix} 1 & \gamma & \gamma & \gamma \\ \gamma & 1 & \gamma & \gamma \\ \gamma & \gamma & 1 & \gamma \\ \gamma & \gamma & \gamma & 1 \end{bmatrix}$$

Statistical Analysis Plan Version: 1.0 Date: 26-Apr-2020

AE represents the occurrence of a hypotensive AE (at least one), during the plasmapheresis procedure. *Treatment* is the variable representing plasmapheresis group (1=Experimental group, 0=Control group). For the *Gender* variable 1=Female, 0=Male. In *First comer* variable 1=First-time donor and 0=Repeat donor. First-time donors are those who have never undergone a plasmapheresis procedure. Age and BMI are continuous variables. i represents subject ID and t represents donation number for the given i subject.

Correlation structure within patients will be assumed to be exchangeable. Derivation of the final correlation model is currently in progress. The correlation structure can also be defined with the use of the historic data from the current study centers.

The above modeling will be used to obtain estimates of difference in proportions of significant hypotensive (vasovagal/hypovolemia) AE rates ($P_{Exper} - P_{Ctrl}$) in experimental and control groups along with its one-sided 97.5% upper limit of the CI calculated with Wald method.

[figure not shown]

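### Donors given the wrong procedure at their first donation are moved to the arm they received, so for them the primary ITT analysis is not by randomised arm, and no planned endpoint analysis restores it

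*SAP*

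**What the plan says.** SAP section 1.2.3 defines the error: "Allocation Miss-Assignment means administration of a study procedure other than that which was provided by the randomization assignment". If it happens at the first donation, the donor continues with the procedure given, and "Their study group assignment will be changed to the administered procedure group". A donor who ends up donating in both groups is discontinued, and "The study group associated with the donor will follow the procedure that the donor administered at the first donation".

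The primary analysis (SAP 3.1) is on the ITT population, and its model has "plasmapheresis method (study group) being fixed effect" (SAP 3.1.1). On adjustment, the SAP states: "Additional covariates are age, gender, BMI, and first-time donor status".

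The SAP's ITT definition is a rule about which donations count: "The ITT data set will consist of all study donations were the apheresis procedure was started". Protocol section 9.1 does the same. Neither says in which arm a donation counts. SAP 2.2.1 defines a Study Donor by the fact of having been randomised, again without tying the analysis to the randomised arm.

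Protocol sections 7.1 and 8.3 say that the original assignment is carried over to later donations. The protocol has no rule for administration errors.

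**The concern.** The SAP changes the study group and then models the study group. For donors mis-assigned at the first donation, the treatment variable in the analysis labelled ITT is therefore an as-received variable. Randomisation no longer protects the comparison for them.

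This matters only if mis-assignment is related to risk in a way that age, gender, BMI and first-time status do not capture. Such errors would put a selection effect into the analysis that carries the non-inferiority claim. With no planned endpoint analysis by randomised arm, a reader could not tell whether the conclusion depends on the relabelled donors. Events are few, so a handful of such donors could matter.

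The scope is limited. A donor treated correctly at the first donation keeps the randomised arm even if an error follows later.

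**Working it through.** **Does any planned analysis restore the randomised arm?**

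- MITT is a subset of ITT and carries the same label.
- PP takes "all donations without major protocol deviations where the apheresis procedure is successfully completed" and adds back donations with moderate or severe events. It may drop mis-assigned donations if the deviation counts as major, which is not defined, but it does not return anyone to the randomised arm.
- The extended AE population adds events and leaves the arm unchanged.
- The optional alternatives in SAP 3.3 vary the model, the test or the interval method.
- Assigned versus actual randomisation appears only as a key risk indicator (protocol 9.8, SAP 3.3), not as an endpoint comparison.
- The safety analysis (SAP 3.5) uses ITT and MITT.

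So none does. One inference is needed: the SAP never states that the Treatment variable holds the changed value. It uses the same term in both places, and nothing says otherwise.

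**Inputs for size.** From SAP section 5: 24,000 donations from 6,000 donors in two equal groups (12,000 donations per arm, 4 per donor), event rate 0.0015, margin 0.0015, one-sided 2.5%. The mis-assignment rate and the relative risk R of mis-assigned donors are assumptions. The calculations use unadjusted Wald limits on independent binomials and ignore covariates and within-donor correlation. SAP Table 1 itself reports 5.7% at the margin, so only the comparisons below are meaningful, not the levels.

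**One donor moved.** Expected events per arm: 12,000 × 0.0015 = 18. The upper limit is d + 1.96 × √[p₁(1−p₁)/n₁ + p₀(1−p₀)/n₀].

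- 24/12,000 − 18/12,000 = 0.000500, upper limit 0.00156: fails.
- Move one experimental donor (1 event, 4 donations) to control: 23/11,996 − 19/12,004 = 0.000335, upper limit 0.00139: passes.
- Shift: 0.000500 − 0.000335 = 0.000165, and 0.000165/0.0015 = 11%.

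Given that one event is moved (denominators held at 12,000) and the true rates are equal at 0.0015, the verdict changes in 6.2% of trials (experimental to control) or 8.7% (control to experimental).

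**Average-risk donors.** Moving one event with 668 donations from 18 v 18 gives 17/11,332 − 19/12,668 = 0.0000003, essentially no change.

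**Selective one-way errors, no true effect.** Assume 1% of donors (60 donors, 240 donations) were randomised to experimental, received control, and have R times the average rate. They contribute 240 × 0.0015 × R = 0.36R events. The relabelled difference is (18 − 0.36R)/11,760 − (18 + 0.36R)/12,240:

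| R | Relabelled | Share of margin | As randomised |
|---|---|---|---|
| 1 | 0 | 0% | 0 |
| 2 | −0.00006 | 4% | 0 |
| 3 | −0.00012 | 8% | 0 |

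With the direction reversed (randomised to control, received experimental), the shifts are +0.00006 and +0.00012, against the experimental arm.

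**Same errors at the margin.** Assume the experimental procedure doubles the rate (0.0030 v 0.0015). The relabelled difference is 2(18 − 0.36R)/11,760 − (18 + 0.36R)/12,240. The as-randomised difference is [2(18 − 0.36R) + 0.36R]/12,000 − 0.0015. Both are compared with 0.0015:

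| R | Relabelled shift | As-randomised shift | False non-inferiority, relabelled v as randomised |
|---|---|---|---|
| 1 | 0 | −0.00003 | 2.9% v 3.2% |
| 2 | −0.00009 | −0.00006 | 4.0% v 3.6% |
| 3 | −0.00018 | −0.00009 | 5.4% v 4.0% |

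**Random two-way crossover at the margin, as randomised.** False non-inferiority is 2.9% with no errors, 3.2% at 1% of donors and 4.8% at 5%.

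**The case against.** Grouping by procedure received is a defensible choice for a safety endpoint tested for non-inferiority. It is unbiased under random error, whereas as-randomised grouping dilutes a true harm and slightly eases the claim. The rule is also explicit, fixed in advance and deterministic. Both points stand, and they are why the remedy asks for both analyses. They do not make the present analysis ITT.

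The one-way scenarios are the unfavourable half. Reversed errors are conservative, balanced errors largely cancel, and nothing in the documents supports a particular direction or R. At the margin, relabelling is worse than as-randomised grouping by only 0.00003 (2% of the margin) at R = 2 and 0.00009 (6%) at R = 3, and at R = 1 it is better. This stands as a limit on the size.

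The 6.2% and 8.7% are conditional on a mis-assigned donor having an event. At 1% mis-assignment and average risk, 0.36 such events are expected, about a 30% chance of any (1 − e^−0.36). The 24 v 18 case is chosen at the boundary. This too stands.

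Controls exist: electronic assignment synchronised with the donor system, sponsor checks of randomisation, arm-specific product codes verified for every subject, separately located devices and a proficiency criterion on group assignment. They may keep the number small. They do not settle which arm a mis-assigned donor is analysed in.

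**Conclusion.** The concern holds. By a stated rule, donors mis-assigned at the first donation enter the primary analysis by procedure received, the analysis is labelled ITT, and no planned endpoint analysis uses the randomised arm for them. This rests on reading the model's study group as the one section 1.2.3 changes, which is the natural reading.

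The likely effect is small: zero if errors are unrelated to risk, and 4% to 8% of the margin in the assumed 1% one-way scenarios with no true effect, in either direction. It could decide a borderline result, because one relabelled donor with an event is worth 11% of the margin. Neither the error rate nor its relation to risk is known. The point should be fixed because the label is wrong as written and the plan gives no way to check its influence.

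**What to change.** In SAP sections 1.2.3, 2.2.2 and 3.1.1:

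- Keep the randomised arm as a variable that is never overwritten, and use it for the analysis labelled ITT.
- Hold procedure received as a separate variable and pre-specify an as-treated analysis beside it, because as-randomised grouping is slightly anti-conservative under random crossover.
- If the sponsor prefers procedure received for the primary safety analysis, give it another name and pre-specify the as-randomised analysis as a sensitivity analysis.
- Either way, keep the success criterion on the single primary analysis.
- Report mis-assigned donors, donations and events by randomised arm and by procedure received.

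SAP 1.2.3 and protocol 7.1 and 8.3 must also be reconciled on which procedure such donors continue with. This review takes no view on that.

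The cost is SAP wording, one retained variable (the randomisation system already holds the code) and one extra model run. The statistical cost of as-randomised grouping is the dilution under random crossover, which the as-treated analysis would expose.

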2. STATISTICAL CONSIDERATIONS

2.1. GENERAL CONSIDERATIONS

Continuous and discrete modeling techniques will be applied whenever applicable. Distribution summaries will be presented through summary tables data and visualization methods. Stratification analysis by each individual site will be presented. The relationship between covariates will be examined by appropriate statistical methods. The analysis will include distributional summaries, summaries of the means/measures of central tendency of the two (control and experimental) groups obtained by different methods.

Analysis will be performed using SAS 9.4 (or higher) statistical software.

2.2. DEFINITIONS OF ANALYSIS DATA SETS

2.2.1. DEFINITIONS

Study Donor is defined as a study participant who consented to the study and was randomized to a study procedure (control or experimental).

Statistical Analysis Plan Version: 1.0 Date: 26-Apr-2020

Study Donation is defined as a donation that took place during the course of the study and is associated with the study donor.

Non-Study Donation is defined as a donation that took place either before the study start date or after the last date of the study.

Study Adverse Event is defined as an adverse event that was reported to be associated with the study donation.

2.2.2. STUDY POPULATIONS

The ITT data set will consist of all study donations were the apheresis procedure was started by "Begin Draw" on the NexSys® PCS device. The ITT population will include all Study Adverse Events.

The Modified Intent to Treat (MITT) data set is a subset of the ITT data set which consists of all complete study donations, as well as all donations associated with a moderate or severe adverse event [not just hypotensive (vasovagal/hypovolemia)] defined according to the IQPP and associated with the study donations. A donation is considered complete if the total plasma volume collected is at least 200 mL. A donation is considered incomplete if the total plasma volume collected is less than 200 mL.

The Per-Protocol (PP) data set will consist of all donations without major protocol deviations where the apheresis procedure is successfully completed collecting at least 90% of the target plasma volume, as well as all study donations associated with a moderate or severe adverse event [not just hypotensive (vasovagal/hypovolemia)] defined according to the IQPP.

Statistical Analysis Plan Version: 1.0 Date: 26-Apr-2020

The Extended AE Population (EAEP) is defined as consisting of ITT population with the addition of all the AEs that were reported as associated with Non-Study donations in donors previously enrolled in the study and reported within two calendar weeks post study last day.

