Hypotensive (Vasovagal/Hypovolemia)     Hypotensive reaction (vasovagal/hypovolemia) that falls into any of the following categories.			
NOTE: For the purposes of this IQPP Standard, "medical staff intervention" means the use of expertise from the physician or physician substitute to make decisions regarding the management of the DAE.			
1.1 Hypotensive: Prefaint, No LOC (Minor)	This reaction:  a. must resolve without medical staff (e.g., physician substitute) intervention, AND  b. Involves signs and symptoms that resolved quickly (e.g. within approximately 10 minutes).	May include one or more of the following:  a. Abdominal cramps; b. Auditory disturbance (e.g. sounds coming from a distance or "buzzing" in the ears); c. Chills or Shivering; d. Clammy; e. Cold extremities; f. Dizziness; g. Epigastric discomfort; h. Facial pallor (e.g. pale skin or lips); i. Feeling of Warmth; j. Headache or neck ache; k. Hypotension; l. Lightheadedness; m. Nausea; n. Palpitations; o. Sweating; p. Visual Disturbance (e.g. blurred or faded vision); or q. Weakness.	

DAE Classification	Description	Signs/Symptoms/Findings
1.2 Hypotensive: Prefaint, No LOC (Moderate):	This reaction:  a. requires medical staff	May include any in 1.1 AND  a. Vomiting.
1.3 Hypotensive: LOC (brief)	In this reaction, LOC lasts approximately less than sixty seconds.	May include any in 1.1 or 1.2.
1.4 Hypotensive: LOC (prolonged)	In this reaction, LOC lasts approximately sixty seconds or longer.	May include any in 1.1 or 1.2.
1.5 Hypotensive; Severe (With or Without LOC):	This reaction may or may not include LOC.	May include any in 1.1 through 1.4 AND any of the following:  a. Chest Pain;  b. Convulsions/Seizures  c. Loss of Bladder/Bowel Control; or  d. Prolonged signs or symptoms that do not resolve.
1.6 Hypotensive; Injury	A hypotensive event that results in ANY type of injury such as:  a. Closed Head Injury; b. Dental Injury; c. Fracture; d. Laceration; e. Soft Tissue Injury (not phlebotomy- related); or f. Other.	May include any of 1.1 – 1.5 as well as any signs/symptoms related to the injury itself.

*NOTE:* If the donor exhibits symptoms of a hypotensive event (1.1 through 1.6), in addition to "anxiety," then the event should be classified according to "1.1 - 1.6 Hypotensive."

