### 9.1 Analysis Data Sets

The primary analysis will be conducted on the Intent to Treatment (ITT) data set. The ITT data set will consist of all donations where randomization was completed and the apheresis procedure was started by "Begin Draw" on the NexSys® PCS device.

Sensitivity analysis may be conducted using a Modified *ITT* (MITT) data set and the per-protocol data set. The MITT data set will consist of all complete donations (see Section 6.1.2), as well as all donations associated with a significant hypotensive (vasovagal/hypovolemia) adverse event according to the plasma center adverse event reporting system, based on the IQPP definitions.

The per protocol data set will consist of all donations where the apheresis procedure was successfully completed collecting at least 90% of target plasma volume as well as all donations associated with a significant hypotensive (vasovagal/hypovolemia) adverse event according to the plasma center adverse event reporting system, based on the IQPP definitions.

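### SAP 2.2.2 puts interrupted donations back into MITT and PP only for a moderate or severe event, so loss-of-consciousness events (IQPP rows 1.3 and 1.4), which are primary events, can drop out of these sets

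*SAP*

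**What the plan says.** Protocol 9.1 starts MITT from complete donations and PP from donations that reached 90% of target. To each it adds donations below the cut that had a primary event: "as well as all donations associated with a significant hypotensive (vasovagal/hypovolemia) adverse event". Protocol 5.1 defines significant as IQPP rows 1.2 to 1.6.

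SAP 2.2.2 keeps the same volume cuts ("A donation is considered incomplete if the total plasma volume collected is less than 200 mL" for MITT, "collecting at least 90% of the target plasma volume" for PP) and also bars major protocol deviations from PP. It changes the event clause. MITT reads "as well as all donations associated with a moderate or severe adverse event" and PP reads "as well as all study donations associated with a moderate or severe adverse event". Both extend to non-hypotensive events and refer to the IQPP for the grading.

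In the IQPP excerpt in Protocol 5.1, the row titles for the events at issue begin "1.2 Hypotensive: Prefaint, No LOC (Moderate", "1.3 Hypotensive: LOC (brief" and "1.4 Hypotensive: LOC (prolonged". Row 1.5 is titled severe and row 1.6 injury. Stopping Rule 2 (Protocol 9.10, SAP 3.6) counts rows 1.5 and 1.6 as severe hypotensive events.

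SAP 3.1 runs the primary analysis on ITT, which holds all study adverse events, and commits to sensitivity analyses on MITT and PP. SAP 3.2 assigns analyses that involve plasma volume to MITT and PP.

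**The concern.** A primary event often ends the draw, so a volume cut removes donations because of the outcome. The event clause exists to undo that. If it covers rows 1.2, 1.5 and 1.6 but not 1.3 and 1.4, a moderate prefaint is restored while a prolonged loss of consciousness is not. Sets built in this way are a poor check on a safety endpoint. If the two arms differ in loss of consciousness, the MITT and PP estimates could look closer together than ITT for a reason that lies only in the wording.

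The analysis of significant hypotensive events by collected volume may also be exposed, because on one reading of SAP 3.2 it runs only on MITT and PP. The missing events would be those at the lowest volumes, which that analysis most needs.

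**Working it through.** **1. Row by row**

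| IQPP row | Primary event | Severity word in the documents | Restored by Protocol 9.1 | Restored by SAP 2.2.2, read literally |
|---|---|---|---|---|
| 1.1 | no | minor (row title) | no | no |
| 1.2 | yes | moderate (row title) | yes | yes |
| 1.3 | yes | none | yes | no |
| 1.4 | yes | none | yes | no |
| 1.5 | yes | severe (row title, Stopping Rule 2) | yes | yes |
| 1.6 | yes | severe (Stopping Rule 2 only) | yes | yes, on the trial's own usage |

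**2. Where the cuts fall.** MITT loses a row 1.3 or 1.4 event only below 200 mL. PP loses it below 90% of target. For the 1992 nomogram volumes (Protocol 1.4) that is 0.9 x 625 = 562.5 mL, 0.9 x 750 = 675 mL and 0.9 x 800 = 720 mL. At the PPN cap it is 0.9 x 1,000 = 900 mL. PP is therefore far more exposed than MITT, and loss from both sets needs less than 200 mL.

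**3. Planned event count.** Inputs from SAP 5: rate 0.0015, margin 0.0015, 24,000 donations (about 12,000 per arm), one-sided 2.5%. As a check on these inputs, a simple two-proportion calculation with independent donations gives SE = sqrt(2 x 0.0015 x 0.9985 / 12,000) = 0.000500. Power is Phi(0.0015/0.000500 - 1.96) = 85.1%, in line with the stated figure above 85%.

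Expected primary events: 24,000 x 0.0015 = 36. Expected severe events at 1/10,000 (SAP 3.2): 24,000 / 10,000 = 2.4, or 2.4/36 = 6.7%. If severe there means rows 1.5 and 1.6, as in Stopping Rule 2, the other 93% lie in rows 1.2 to 1.4. The documents do not split them further.

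**4. Events lost.** Lost = 36 x (share in rows 1.3 and 1.4) x (share of those below the cut). Both shares are assumptions.

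| Share in rows 1.3/1.4 | 10% below cut | 25% below cut | 50% below cut |
|---|---|---|---|
| 10% | 0.4 | 0.9 | 1.8 |
| 25% | 0.9 | 2.3 | 4.5 |
| 50% | 1.8 | 4.5 | 9.0 |

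With 90% below the cut, plausible only for PP, the top figure is 36 x 0.5 x 0.9 = 16.2.

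**5. What one event can do.** Upper limit = d + 1.96 x sqrt[pE(1 - pE)/12,000 + pC(1 - pC)/12,000], where d = pE - pC, with 18 control events.

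- 24 experimental events: d = 0.00050, SE = 0.000540, limit 0.00156. Non-inferiority is not shown.
- 23 experimental events: d = 0.00042, SE = 0.000533, limit 0.00146. Non-inferiority is shown.

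This treats donations as independent, keeps 12,000 per arm although PP would have fewer, and is not the planned GEE model. The counts were chosen to sit at the margin.

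**The case against.** The best defence is that moderate or severe was meant as more than minor. Only row 1.1 is called minor, the SAP treats it separately (SAP 3.3), and extending the clause to non-hypotensive events suggests that the aim was to widen it. The full IQPP standard is an attachment not reproduced here, so how it grades loss of consciousness cannot be checked. This stands in part. The clause is unclear and departs from Protocol 9.1, but an intended exclusion is not shown. A programmer working from the two documents would still find no text that restores rows 1.3 and 1.4.

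Three stronger readings are tempting, and the documents do not support them.

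- *That injury events are lost too.* The title of row 1.6 has no severity word, but Stopping Rule 2 calls it severe in both documents. At most this is an ambiguity.
- *That these events generally leave both sets.* Between 200 mL and 90% of target they leave PP only.
- *That the trial could wrongly declare non-inferiority.* The decision rests on ITT, which keeps every event, and nothing lets MITT or PP overturn it. SAP 3.5 also tabulates events by IQPP category and arm on ITT, so an excess in loss of consciousness would be seen there.

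Two further points are fair. Protocol 2.4 places peak extracorporeal volume at full collection and ties intravascular deficit to the end of the procedure. Events that late would already meet the 90% cut, so a high share below it cannot be presumed. And Protocol 9 lets the SAP modify its plans, so the departure is permitted. It is, however, given no reason.

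**Conclusion.** The point holds as a conflict between Protocol 9.1 and SAP 2.2.2 that, on the literal SAP wording, can remove row 1.3 and 1.4 events from PP (below 90% of target) and from both sets (below 200 mL). The primary result, sample size and power are untouched. What is weakened is the robustness check promised in SAP 3.1 and, on one reading of SAP 3.2, the analysis of events by collected volume.

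The size cannot be derived from the documents. The range of about 0.4 to 9 of 36 events rests on two assumed shares of 10-50% each. The one-event example shows only that a small loss can change a sensitivity result when the data lie near the margin. It does not show that this is likely.

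**What to change.** In both definitions in SAP 2.2.2, replace the event clause with: *all study donations with a significant hypotensive adverse event (IQPP rows 1.2 to 1.6)*, as in Protocol 9.1. If non-hypotensive events are also to count, list them by IQPP row and say that this goes beyond the protocol.

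The cost is one sentence per data set, best made before unblinded data are seen. The hypotensive clause needs no protocol amendment, since it returns the SAP to the protocol. By construction, no primary event can then fall out of MITT or PP because of the volume collected.
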